9.1 Subject Authorization for Use and Disclosure of Protected Health Information (PHI)

The Investigator must ensure that written authorization for use and disclosure of protected health information is obtained before including any individual as a subject in the study.

Specifically, the Investigator is to explain to each subject all elements of authorization as specified in 45 CFR 164.508. After the explanation, the subject or legally authorized representative must voluntarily sign and date the authorization form if they wish to participate in the study. A copy of the authorization form must be provided to the subject or legally authorized representative. A signed and dated copy of the authorization form must be maintained in the Investigator Site File at all times and may be placed in the subject's medical record.

An authorization form may be combined with a consent/assent form (i.e. compound authorization) if required by the IRB. All required elements for both informed consent/assent and authorization must be included in a compound authorization.

9.2 Subject Revocation of Authorization to Use and Disclose Personal Health Information

In order to implement a valid revocation of authorization, the subject or their legally authorized representative must make the request in writing to the [Institution name and address]. The revocation cannot stop the use or disclosure of information that has been collected prior to the revocation, is needed to ensure complete and accurate study results, or is required by law or government regulation (e.g. reporting adverse events, etc.). Revocation of an authorization may not be used to withhold normal medical care from the subject, but may [or will] make the subject ineligible to receive study care.

9.3 Informed Consent in Regards to Decisionally Impaired Persons

The Principal Investigator and approved members of the study team will use their clinical judgment to assess if a potential participant is decisionally impaired. If a participant is found to be decisionally impaired, but is eligible for the study, the study team will seek consent from the legally authorized representative or next of kin. If the subject is capable of consent/assent, consent/assent of the subject will be obtained before they are entered into the study.

If a subject, previously determined to lack capacity to consent/assent, regains capacity during the study, the Investigator must obtain the consent/assent of the individual for the remaining part of the study.

9.4 Confidentiality of Data

The Principal Investigator will oversee the conduct of the study and all data will be kept confidential. Confidentiality will be maintained by using patient identification numbers instead of names. Consent forms, data collection sheets and records, linking a subject's name with their ID number will be maintained in a locked cabinet or locked office. Information to be stored on the computer will be identified by subject ID and will be password protected. Data disclosed outside the study team will be de-identified or will only include general group demographic information. Protected Health Information and/or identifiable study data will not be shared with anyone outside the study team or Health System, with the exception of the study sponsor, and federal regulators/ institutional officials for the purposes of auditing.

10. Screening and Enrollment

Subjects enrolled Week 1 will follow the following application/assessment schedule: M-W-F, T-TH-SAT, W-F or Th-Sat.

Week 2 and Week 3 application/assessment schedule will always follow M-W-F schedule. Subjects enrolling later in the week will need to be followed up by study coordinators for application 9 (M) in Week 4.

A representative from the site will complete the following screening and enrollment activities:

- Obtain Informed Consent
 - Explain the study to the subject, answer questions, and obtain written informed consent
- Review the Inclusion/Exclusion Criteria.
- Perform assessments required by the Inclusion/Exclusion criteria.
 - Collect urine sample and perform urine pregnancy test for female subjects who are of childbearing age. If the subject is post-menopausal, no pregnancy test is required.

3M is using the IAD Severity Categorisation Tool from Beeckman D et al Proceedings of the Global IAD Expert Panel (2015) for current classification of IAD. Attached below is Table 1, IAD Severity Categorisation Tool displaying the severity of IAD and associated signs for the study investigators use in categorizing subjects. Only subjects with a Category 2 level of IAD will be enrolled into this study.

TABLE 1 | IAD Severity Categorisation Tool

Clinical presentation	Severity of IAD	Signs**
	No redness and skin intact (at risk)	Skin is normal as compared to rest of body (no signs of IAD)
	Category 1 - Red* but skin intact (mild)	Erythema +/-oedema
	Category 2 - Red* with skin breakdown (moderate-severe)	As above for Category 1 +/-vesicles/bullae/skin erosion +/- denudation of skin +/- skin infection

If a subject does not meet all the Inclusion/Exclusion criteria, and is excluded from the study, the reason(s) for exclusion will be documented on the Screening Log.

If a subject meets all the Inclusion/Exclusion criteria, the Investigator or study nurse will obtain and open the randomization envelope to determine which product group the subject has been assigned to. The study nurse will complete the following remaining screening activities:

- Record subject demographics.
- Obtain and record IAD history.
- Obtain and record information describing current medications and IAD treatment.
 - Oral or systemic medications prescribed by the subject's physician are allowed and will be noted on the appropriate CRF.

- Incontinence-related devices (such as urinary catheters, pads, diapers, etc.) are allowed and will be noted on the appropriate CRF.
- Use of moisture barrier, creams, ointments, pastes, or other topical medications in combination with the Cavilon Advanced Skin Protectant product for the management of IAD is **not** allowed.
- If subjects had prior barrier film products on their skin, use the Brava Adhesive Remover Wipe.
- Conduct pressure ulcer risk assessment using Braden Scale.
- Administer Quality of Life questionnaire.
- Perform skin cleansing:
 - Use 3M[™] Cavilon[™] No-Rinse Skin Cleanser (to be provided by 3M) or warm tap water and soft cloths.
 - Avoid rigorous scrubbing to minimize friction damage.
 - Record pain score assessment using Faces Pain Scale Visual Analog before and after cleansing for adults or the FLACC scale for pediatrics during the cleansing process.
- Conduct skin assessment:
 - Complete a skin assessment of the following six zones for its color, presence of lesions, and skin loss. Only subjects with denuded skin may be enrolled. The IAD score will be calculated electronically once results are entered into computer system using 3M's validated Skin Condition Assessment Tool (see Appendix A).
 - Zone 1: Includes the anus and 2 inches surrounding anal opening plus: for males score the scrotal sac and females the labia majora.
 - Zone 2: Crease between buttocks, above the anal opening and 2-3 inches below natural waistline
 - Zone 3: Left buttock starts above fold between thigh and buttock and extends upward to 2-3 inches below natural waistline
 - Zone 4: Left Posterior and medial upper thighs
 - Zone 5: Right buttock starts above fold between thigh and buttock and extends upward to 2-3 inches below natural waistline
 - Zone 6: Right Posterior and medial upper thighs

The score for each of the six (6) body zones will then be combined to obtain a single IAD score for the subject.

• Take photographs:

- Position the subject appropriately in order to capture all affected body zones.
- Take photograph including a paper ruler in the picture.
- o Download photographs immediately to the EDC system.
- Biomedical Systems is an outside vendor who will QC the photographs for correcting the color quality.

11. Study Assessments

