6.2 Blinding

Given the obvious differences between a paste versus a liquid delivered in an applicator, and the fact that the skin protectant paste can leave visible residues even after cleansing, the study nurse applying the products cannot be blinded.

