7.1 Primary Efficacy Endpoint

The primary efficacy endpoint will be percent change in IAD score from baseline to end of subject participation. The effect of skin protectants on clinical re-epithelialization of denuded skin in subjects with containment or resolution of urinary and/or fecal incontinence, as well as in subjects with ongoing urinary and/or fecal incontinence, will be observed. Skin condition will be determined using

clinical assessment data collected by means of a validated IAD skin assessment tool, and photographs.

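### Section 10 opens the randomization envelope before the scored six-zone baseline assessment and photographs, so the denominator of the primary percent-change endpoint can be rated with the arm known

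*Combined protocol and SAP*

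**What the plan says.** Section 10 (Screening and Enrollment) sets an order. First come consent, review of the criteria, and the assessments that the criteria need. These include judging whether the subject has Category 2 IAD with denudation (Section 8.1, item 3). If the criteria are met, "the Investigator or study nurse will obtain and open the randomization envelope to determine which product group the subject has been assigned to". The text continues: "The study nurse will complete the following remaining screening activities".

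The list that follows contains the quality-of-life questionnaire, cleansing with pain scores, the skin assessment of six zones, and the photographs. Within the skin assessment the protocol repeats an entry condition, "Only subjects with denuded skin may be enrolled", and says of the zone ratings that "The IAD score will be calculated electronically once results are entered into computer system". The zone scores "will then be combined to obtain a single IAD score for the subject". For the photographs the instruction is "Download photographs immediately to the EDC system", and a vendor checks colour quality.

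Section 7.1 makes this score the base of the primary outcome: "The primary efficacy endpoint will be percent change in IAD score from baseline to end of subject participation". Section 6.2 gives the reason for not blinding: the two products look different and "the skin protectant paste can leave visible residues even after cleansing, the study nurse applying the products cannot be blinded".

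The Schedule of Events shows IAD scoring at Screening/Enrollment and again on D1. The CRF table in Section 16.3 puts the initial skin assessment under Screening & Enrollment. No section says which score is the baseline for percent change.

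**The concern.** Percent change divides by the baseline score. That score comes from a nurse's visual judgement of area bands, and in Appendix A one band of epidermal loss in one zone is worth 30 points. If the rater knows the arm and tends to score one arm higher at baseline, that arm shows a larger percent fall in every subject who does not heal completely, with no treatment effect behind it.

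The reason in Section 6.2 does not reach this measurement. Before the first study application there is no product or study paste residue to see, so the baseline can be rated without knowledge of the arm simply by rating it first. Baseline pain and quality of life sit in the same list after opening and are exposed in the same way, though less seriously for quality of life, which the nurse only administers.

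**Working it through.** **1. Order of events.**

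| Step in Section 10 | Relative to envelope |
|---|---|
| Consent, criteria review, Category 2/denudation judgement | before |
| Envelope opened | – |
| Quality of life; cleansing with pain scores | after |
| Six-zone ratings that give the IAD score | after |
| Photographs | after |

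The Schedule of Events and the CRF table do not place scoring before opening, and a D1 score would also follow it. The Investigator may be the one who opens the envelope, so that the nurse knows the arm is an inference. Nothing in the plan prevents it.

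**2. Do other provisions mask the ratings?** Electronic calculation works on ratings already made. Photograph upload and colour checking involve no masked reading. CRF monitoring (Section 16.1) checks completeness and consistency. No masked assessor is named.

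**3. The plan's own figure.** Section 19.2 gives SD 70, difference 45 and 51 per group. SE = 70 × √(2/51) = 13.86, and 45/13.86 = 3.246. Power by the normal approximation is Φ(3.246 − 1.960) = 90.1% at two-sided 0.05, and Φ(3.246 − 1.975) = 89.8% at the final level of 0.0483 (Section 19.3). The stated power of at least 80% is true, and the order of assessments does not affect it.

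**4. Shift per subject.** Assumptions: zone scores are summed (the text says only that they are combined), one extra band (+30) is scored at baseline, and the last score is unaffected. Example scores are assumed, because the documents give no baseline distribution. Percent change = 100 × (last − base)/base.

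| Base to last | True | With base + 30 | Shift (points) |
|---|---|---|---|
| 60 to 0 | −100.0 | −100.0 | 0 |
| 360 to 180 | −50.0 | −53.8 | 3.8 |
| 240 to 120 | −50.0 | −55.6 | 5.6 |
| 120 to 60 | −50.0 | −60.0 | 10.0 |
| 60 to 30 | −50.0 | −66.7 | 16.7 |
| 60 to 60 | 0.0 | −33.3 | 33.3 |
| 30 to 30 | 0.0 | −50.0 | 50.0 |
| 60 to 120 | +100.0 | +33.3 | 66.7 |

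**5. Shift in the arm mean and false-positive rate.** Let f be the share of one arm over-scored and h the share of those who heal to 0. Arm-mean bias b = f × (1 − h) × shift. With no true effect, the rejection rate of the final test is Φ(b/13.86 − 1.975) + Φ(−b/13.86 − 1.975). This takes the SD as unchanged and considers the final test alone.

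| Example | f = 10%, h = 0 | f = 50%, h = 0 | f = 50%, h = 50% |
|---|---|---|---|
| 360 to 180 | b 0.4: 4.8% | b 1.9: 5.0% | b 1.0: 4.9% |
| 120 to 60 | b 1.0: 4.9% | b 5.0: 6.3% | b 2.5: 5.2% |
| 60 to 30 | b 1.7: 5.0% | b 8.3: 9.0% | b 4.2: 5.9% |
| 60 to 60 | b 3.3: 5.5% | b 16.7: 22.1% | b 8.3: 9.0% |

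The nominal rate is 4.83%. A rate of 6% needs b = 4.46 points. As a share of the arm over-scored and not healed, that is 4.46/33.3 = 13% for 60 to 60, 4.46/16.7 = 27% for 60 to 30, 4.46/10.0 = 45% for 120 to 60 and 4.46/5.6 = 80% for 240 to 120. It cannot be reached for 360 to 180 (4.46/3.8 exceeds 1).

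**The case against.** The best reply is that the larger exposure lies elsewhere. Follow-up scores are rated by staff who know the arm and, in the paste arm, may see residue. Someone inclined to favour a product can shade the last score whatever happens at baseline. That stands, and it limits the gain from reordering. It does not justify leaving open the one measurement that order alone can protect.

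The figures also depend on the examples. A baseline of 30, or a subject who worsens, shifts much further than most rows above, and a ranked analysis, which Section 19.1.1 allows, is not modelled. The 22.1% needs half of one arm over-scored by a full band with no true change in any of those subjects. The tables show when the effect would matter; they neither estimate nor bound it.

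There are partial checks. A dated photograph would let a gross over-score be questioned, and monitors review the CRFs. These may deter, but they do not mask.

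A reader might infer that sites inflated baseline scores, or that entry itself was decided with the arm known. The documents support neither. They contain no sign of over-scoring. Category 2 with denudation must be judged before opening, so the repeated denudement line need not be a fresh decision on entry.

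**Conclusion.** The concern holds as a weakness in sequence. As written, the baseline IAD score can be rated with the arm known, and no provision prevents that. Its effect is zero for subjects who heal to 0, small if few subjects are over-scored, and material only if over-scoring in one arm is common. This rests on summed zone scores, a one-band error and assumed example scores. It is worth fixing because the remedy is cheap, not because bias has been shown.

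It does not follow that the primary result would be invalid. Nor does the order of steps settle what happens to a treated subject later judged not denuded. That turns on a conflict between the Synopsis, which limits the primary set to eligible subjects with a post-baseline assessment, and Section 19.1.1, which takes all subjects with at least one dose. It is a separate matter to reconcile.

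**What to change.** Reorder Section 10 so that the following are complete before the envelope is opened: baseline cleansing with its pain scores, the quality-of-life questionnaire, the six-zone ratings and the photographs. The ratings should be signed and time-stamped on the data sheet or in the EDC (Section 16.3 allows either). The stamp belongs on the ratings because the score is calculated later. Confirm denudement from that assessment, then open the envelope. State that this Screening/Enrollment score, and not the D1 score, is the baseline for percent change.

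The cost is a protocol edit, retraining at about 13 sites, and one added signature and time stamp per subject. The study began in fall 2015 and this is version 7 of August 2016, so only subjects randomized after the change are protected. Baseline procedure will differ by enrolment date, and the report must disclose this. Sample size and power are unchanged, and follow-up scoring remains unblinded.

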11.1 Investigational Product Group and Comparative Group

The following assessments will be completed 3 times per week (i.e. on dosing days M-W-F or T-Th-Sat, W-F or TH-Sat) for subjects enrolled:

• Perform Skin Cleansing

- o Use 3M[™] Cavilon[™] No-Rinse Skin Cleanser or warm tap water and soft cloths.
- Avoid rigorous scrubbing to minimize friction damage.
- Record pain score using Faces Pain Scale Visual Analog for adults or FLACC scale for pediatrics
- Time and Motion (Completed on one subject in each product group at each site)
 - $\circ\,$ This should be done after you have experience with applying both products. Preferably dose 2 or later
 - Document the time taken to cleanse the skin during a fecal incontinence episode
 - Document the amount of supplies needed to cleanse the skin, as well as the cleansing procedures employed
 - Record pain score using Faces Pain Scale Visual Analog for adults or FLACC scale for pediatrics during cleansing and at product application.

• Conduct Skin Assessment

- Complete a skin assessment of the following six zones for its color, presence of lesions, and skin loss.
 - Zone 1: Includes the anus and 2 inches surrounding anal opening plus: for males score the scrotal sac and females the labia majora.
 - Zone 2: Crease between buttocks, above the anal opening and 2-3 inches below natural waistline
 - Zone 3: Left buttock starts above fold between thigh and buttock and extends upward to 2-3 inches below natural waistline
 - Zone 4: Left Posterior and medial upper thighs
 - Zone 5: Right buttock starts above fold between thigh and buttock and extends upward to 2-3 inches below natural waistline
 - Zone 6: Right Posterior and medial upper thighs

- IAD score will be calculated using 3M's validated Skin Condition Assessment Tool (see Appendix A)
- Take Photographs
 - Position the subject appropriately in order to capture all 6 zones of the buttocks.
 - Take the photograph including the paper ruler in the picture.
 - o Download photographs immediately to the EDC system for review by CRA.
- Medications
 - o Review and record changes to current medications.
- Adverse Events
 - Assess and record adverse events. Immediately report any Serious Adverse Event. (Refer to Adverse Event CRF instructions).
- Incontinence Episodes Care and Tracking
 - At each incontinence care episode, cleanse the skin with 3M[™] Cavilon[™] No-Rinse Skin Cleanser or warm tap warm with soft cloths. Gently dry. Avoid rigorous scrubbing to minimize friction damage.
 - Do not reapply Cavilon Advanced Skin Protectant between each incontinence cleansing episode. Follow the dosing schedule of either:
 - M-W-F, T-TH-Sat, W-F or TH-Sat for week 1. Week 2 &3 follow M-W-F.
 - For the comparative arm product must be applied at every incontinence cleansing episode.
- Healthcare Worker Ease of Use Survey (only after first dosing)
 - Complete product Ease of Use survey following application of Cavilon Advanced Skin Protectant
- Cavilon Advanced Skin Protectant Product Application
 - Following cleansing, the 3M[™] Cavilon[™] Advanced Skin Protectant will be applied 3 times a week following the M-W-F dosing schedule.
 - A thin coat of the Cavilon Advanced Skin Protectant will be painted on or dabbed onto the area covering the entire 6 zones. The Cavilon Advanced Skin Protectant product contains 2.4 mL of material which can cover a maximum area of 25 cm X 25 cm or 10 inches X 10 inches.

- More than one applicator may be necessary depending on the surface area involved. In the event that the contents of one applicator are not sufficient to cover the area requiring protection, additional applicators can be used as needed. Record the number of applicators used.
 - For subjects with IAD in the perineal area (front of body), the same product (either Cavilon Advanced Skin Protectant or comparative product) should be applied in the perineal area. This area will not be graded for IAD, but application of product in this area will be noted on the case report forms and the number of applicators used for the perineal area will be tracked separately from the applicators used on the buttocks.
- If there should be a need for product removal, use adhesive remover and gently wipe the area.
- Document the amount of product required to cover the entire affected area
- Record pain score using Faces Pain Scale Visual Analog before and after product application
- Clean Trace ATP System Evaluation after Sensi-Care Product Application
 - After all photos, patient assessments and after product application are completed, the Sensi-Care tube of paste used will be swabbed for environmental contamination using 3M Clean Trace ATP System.

• ConvaTec Sensi-Care® Protective Barrier Paste Application

- ConvaTec Sensi-Care® Protective Barrier Paste, which will be provided by 3M, will be applied after each incontinence episode, per the manufacturer's instructions, during the 21 day follow-up period following cleansing of the skin.
- Use enough product to cover the affected area and beyond the margins.
- For subjects with IAD in the perineal area (front of body), the same product (either Cavilon Advanced Skin Protectant or comparative product) should be applied in the perineal area. This area will not be graded for IAD, but application of product in this area will be noted on the case report forms and the amount of product used for the perineal area will be tracked separately from the amount of barrier paste used on the buttocks.
- Record pain score using Faces Pain Scale Visual Analog before and after Sensi-Care application.

• Study Duration – 3M Cavilon Advanced Skin Protectant

- Subjects can remain in the study for up to 21 days following enrollment. If the subject is discharged prior to 21 days, the subject will still have met the requirements for study completion.
- If the subject no longer has incontinence and heals completely with scores of normal healthy skin before 21 days, they can be discontinued from the study as completing the study.
- Adult or pediatric subjects randomized to the Cavilon Advanced Skin Protectant product group, who either re-epithelialized or have a positive reduction in their IAD during the 21day period, but remain hospitalized and continue to have incontinence, may continue to receive the Cavilon Advanced Skin Protectant product for up to an additional 21 days to evaluate prevention of IAD reoccurrence.

• Pediatric subjects that fail to improve (IAD) within 3 days while on the Cavilon Advanced Skin Protectant product may be discontinued.

• Study Duration- ConvaTec Sensi-Care® Protective Barrier Paste Group

- Subjects can remain in the study for up to 21 days following enrollment. If the subject is discharged prior to 21 days, the subject will still have met the requirements for study completion.
- If the subject no longer has incontinence and heals completely with scores of normal healthy skin before 21 days, they can be discontinued from the study as completing the study.
- Adult subjects randomized to the comparative group, who fail to reach healing at the end of 21-day period with ongoing incontinence may be crossed over to Cavilon Advanced Skin Protectant group and allowed to continue for up to an additional 21 days.
- Pediatric subjects that fail to improve (IAD) within 3 days while on the comparative product may be crossed over to Cavilon Advanced Skin Protectant. The staff should cleanse the skin, complete skin assessments, and photographs prior to application of Cavilon Advanced Skin Protectant.

Additional Observation

• Observe all 6 zones for any signs of fungal infections and /or pressure ulcers.

